2.3.1. Protocol Risk Mitigation Features

Methods to minimize potential risks are relevant for participants assigned to LY3209590 Algorithm 1 and insulin degludec treatment groups. These include:

- Thorough training on the protocol design elements and inclusion/exclusion criteria; use of an electronic diary (eDiary), a web-interface, and reporting system along with availability of associated instruction manuals and reference documents.
- Careful data validation: After patient-reported data has been entered and synced remotely to the central web server, the investigator is able to view the data through the web portal and generate summary reports. An important feature of the study requires careful review of the reported information with the patient and verification of its accuracy at each study visit.
- Email notification to investigator any time the patient reports a potential severe episode of hypoglycemia (requiring assistance due to neurological impairment) in the eDiary.
- Specific criteria for fasting or persistent hyperglycemia are described protocol Section 6.1.2.3.
- Use of CGM with appropriate low/high glucose alarms throughout the study.

Importantly, in both treatment groups, the final dosing decisions remain subject to clinical judgement of the investigator. Decisions to override an algorithm recommended dose are documented in the electronic case report form (eCRF) for Algorithm 1 and insulin degludec.

3. Objectives and Endpoints

Objectives	Endpoints
Primary	

 To investigate the efficacy of LY3209590 compared with insulin degludec in study participants with T1DM 	
 HbA1c change from baseline to Week 26
Secondary	
Efficacy 
 To investigate the efficacy of LY3209590 compared with insulin degludec in study participants with T1DM 	
 HbA1c change from baseline to Week 12 Fasting glucose change from baseline to Weeks 12 and 26 Insulin dose change for bolus insulin from baseline to Weeks 12 and 26
Safety 
 To investigate the safety of LY3209590 compared with insulin degludec in study participants with T1DM 	
 Incidence and rate of hypoglycemia events during the treatment period Incidence of treatment-emergent serious AEs
Pharmacokinetics 
 To characterize the PK of LY3209590 in study participants with T1DM 	
 LY3209590 population-based parameters, such as AUC within dosing interval at Weeks 12 and 26
Tertiary/Exploratory	

 To establish the equivalent dose of LY3209590 relative to insulin degludec To investigate the safety and tolerability of LY3209590 compared with insulin degludec in study participants with T1DM 	
 Insulin dose at baseline and Week 26 Treatment-emergent AEs Incidence and rate of hypoglycemia events during the post-treatment follow-up period Discontinuation of IP due to AEs Clinical laboratory results Systematic assessment of injection site reactions Insulin dose for prandial as well as basal insulin during treatment period and follow-up period Incidence and rate of hypoglycemia during treatment and follow-up period

Objectives	Endpoints
	
 • Incidence and rate of daytime hypoglycemia • Liver aminotransferase change from baseline to Weeks 12 and 26 • Triglyceride and FFA change from baseline to Weeks 12 and 26 • Body weight change from baseline to Weeks 12 and 26

 • To explore quality of glycemic control compared with insulin degludec using CGM 	
 • Glucose time in target range, time in hyperglycemia, time in hypoglycemia • Duration of hypoglycemic events

 • To establish the relationships between dose/exposure and key safety and efficacy measures for LY3209590 	
 • LY3209590 exposure-response relationships for key efficacy and safety measures (e.g., glycemic control, hypoglycemia and safety labs).

 • To characterize the effects of LY3209590 on exploratory PD biomarkers • To explore the development of LY3209590 ADAs • To explore the compliance with the dosing regimen 	
 • Lipids (cholesterol, LDL, HDL, triglycerides) • 6-point SMBG glucose profiles • Biomarkers of lipolysis (FFA) • The frequency of antibody formation to LY3209590 and relationship to safety and efficacy markers will be determined • Incidence and percentage of missed doses of LY3209590 and insulin degludec.

Abbreviations: ADA = antidrug antibodies; AE = adverse events; AUC = area under the curve; CGM = continuous glucose monitoring; FFA = free fatty acids; HbA1c = glycated hemoglobin; HDL = high density lipoprotein; IP = investigational product; LDL = low density lipoprotein; PD = pharmacodynamics; SMBG = self-monitoring blood glucose; T1DM = type 1 diabetes mellitus.

4. Study Design

4.1. Overall Design

Study I8H-MC-BDCP (BDCP) is a multicenter, randomized, open-label, parallel, comparator-controlled Phase 2 study with 3 study periods. The study is designed to evaluate the efficacy and safety of LY3209590 compared with insulin degludec in patients with T1DM treated with MDI for at least 3 months prior to screening.

The study will consist of 3 periods:

- Study Period 1: screening and lead-in period, approximately 2 weeks
- Study Period 2: treatment period, 26 weeks
- Study Period 3: safety follow-up period, 5 weeks

The study schema is presented in Section 1.2.

Study governance considerations are described in detail in Section 10.1.

4.1.1. Study Visits

Study Period 1: Screening and Lead-in

The purpose of procedures at screening is to establish eligibility for inclusion in the study (see Sections 5.1 and 5.2). During this period (upon signing the informed consent form [ICF]), study participants will be trained on disease monitoring and disease management procedures, study diaries, and study procedures.

Electronic participant diaries and participant paper note sheets will be dispensed at Visit 2 and as specified in the Schedule of Activities (Section 1.3) for future visits. Collection of baseline self-monitoring blood glucose (SMBG) profiles via continuous glucose monitoring (CGM) will start at Visit 2. Participants will continue on their same regimen of basal and short acting insulin during the lead-in period up to randomization.

A participant will be considered ineligible and will be discontinued from a trial before randomization if they:

- initiate agents that are prohibited (Section 6.5), or
- initiate insulin pump treatment (Section 5.2)

For all study participants meeting study entry criteria, the Dexcom G6® CGM device will be inserted and activated at (Visit 2). The CGM sensor, transmitter and receiver will be distributed to the participant as needed per the Schedule of Activities (Section 1.3).

SMBG:

Participants will record two 6-point glucose profiles (using the CGM device) at non-consecutive days between Visit 2 and Visit 3. The profile should include readings before and 2 hours after each major meal of the day (breakfast, lunch, and dinner).

Continuous Glucose Monitoring (CGM)

A standard system, Dexcom G6, will be used according to manufacturer's directions for CGM in an unblinded mode. The study participants will wear this device beginning at Visit 2, as shown

in the Schedule of Activities (Section 1.3). In addition, all study participants will be allowed to use their personal blood glucose (BG) meters for additional BG testing, or for taking SMBG measurements during the outpatient period. Therapeutic decisions will be based on the CGM readings. Blood glucose meters must not be used to calibrate the CGM device. CGM calibration must be done using the code provided with each sensor. Participants must use the study-specific CGM receiver and are not allowed to connect the transmitter of the CGM system to a personal smartphone to ensure data availability for download from the receiver at the respective visits as described in the Schedule of Activities (Section 1.3).

At Visit 2, study participants who fulfill eligibility criteria will be trained on the use of the CGM device, CGM sensor replacement, interpretation of CGM-based BG values and alarms, and the requirements for CGM. For the first CGM session, study participants meeting all study-entry criteria will have the CGM sensor inserted as part of the Visit 2 activities.

Study Period 2: Treatment Period

Randomization

Participants who continue to be eligible for the study will be randomized to 1 of the 2 treatment groups. All measures, including a urine pregnancy test, to be performed at Visit 3 (see Schedule of Activities, Section 1.3) should be done prior to injection of the participant's assigned investigational product (IP) to ensure that appropriate baseline measurements are obtained. The participant will begin IP if the urine pregnancy test is negative. If the result of the serum pregnancy test is positive, the participant will be discontinued from the study (see Section 7.2).

Study personnel will inject the first dose of IP at the study site. The PK sample and electrocardiograms (ECGs) at randomization must be collected as described in the Schedule of Activities (Section 1.3).

Treatment

Following randomization at Visit 3, participants will participate in a 26-week treatment period.

For patients randomized to the LY3209590 arm the following guidance for IP administration is applicable:

- During Weeks 0 to 8, site personnel will administer IP at the site. Participants will receive education and training on how to self-administer IP (for details, see the Schedule of Activities). The training should include information on reconstitution of IP, appropriate injection site locations, injection technique, and the signs and symptoms of local adverse reactions, should those occur.
- During Weeks 9 to 12, IP will be reconstituted and administered at the site by the participant, under supervision of trained site personnel to assure that the participant is capable of self-administration.
- During Weeks 13 to 25, outside of titration visits IP can be self-administered by the participant at home unless local regulations require administration at the site, or optionally can be administered once weekly by site personnel.
- Information on self-injection can be reviewed as necessary throughout the study. Additional visits to ensure correct dosing, titration, and study drug administration can occur anytime during the study if deemed necessary by the investigator.

LY3209590 will be administered as follows:

- Algorithm 1 (paper algorithm): dose adjustment guidance provided; study participant will receive an individualized LY3209590 loading dose on Day 1 with weekly adjustments based on fasting glucose (FG) and hypoglycemia data for the first 12 weeks, then every 4 weeks.

For patients randomized to LY3209590 Algorithm 1, documented guidance for dose adjustment is provided (Section 10.8).

For patients randomized to the insulin degludec arm the following guidance for administration is applicable.

Insulin degludec will be self-administered daily by participants after a training and first administration under site personnel supervision on Day 1 according to a modified Riddle algorithm (Section 10.8).

General considerations

Study procedures will be performed as listed in the Schedule of Activities (Section 1.3).

To allow timely sampling for PK assessments, visits for collection of the samples will be scheduled within the required time windows provided in the Schedule of Activities (Section 1.3).

Participants will continue to use concomitant short-acting insulin throughout the treatment period. Discontinuation or changes to regimen are not permitted, except in situations where dose adjustment is required for medical reasons or when allowed per study protocol (see Section 6.5).

Study participants will be instructed to document fasting glucose (FG) each day in their electronic diary (eDiary) by using the values displayed on their CGM device after wakening. In addition, two 6-point SMBG profiles (prior to and 2 hours after the morning, midday, and evening meals) should be done on nonconsecutive days in the week prior to the required visits noted in the Schedule of Activities (Section 1.3).

Participants who develop severe, persistent hyperglycemia based on prespecified thresholds (see Section 6.1.2.3) will receive an unscheduled intensification of their insulin treatment based on clinical judgment of the investigator with a parallel information of Lilly Medical by email.

Participants who need unscheduled intensification of their insulin treatment will continue on IP in the trial until they complete all study visits.

Study Period 3: End-of-Treatment and Safety Follow-up, Visits 20, 801, Early Discontinuation 1 and 2 (ED1 and ED2)

All randomized participants should have a comprehensive efficacy and safety evaluation approximately 1 week after the last dose of LY3209590 and 1 day after the last dose of insulin degludec, and a safety follow-up visit approximately 6 weeks after the last dose of LY3209590 and 5 weeks after the last dose of insulin degludec. During the safety follow-up study period, participants will continue CGM and will be switched back to their previously used basal insulin therapy if appropriate (see Section 6.7.1). Participants will also be required to return any remaining used or unused IP at Visit 20 and the eDiary at Visit 801 to the investigative site.

Participants who *complete the treatment period* will have a comprehensive End-of-Treatment efficacy and safety assessment (Week 26; Visit 20) approximately 1 week after the last dose of

LY3209590 and 1 day after last dose of insulin degludec and a safety follow-up assessment (Visit 801) approximately 6 weeks after the last dose of LY3209590 and 5 weeks after the last dose of insulin degludec.

Participants who *discontinue IP prior to completion* of the treatment period for any reason should follow the visit schedule off study drug and also have a comprehensive End-of-Treatment efficacy and safety assessment (ED 1) approximately 1 week after the last dose of LY3209590 and 1 day after the last dose of insulin degludec or as soon as reasonably possible thereafter, and should have a safety follow-up assessment (ED 2) approximately 6 weeks after the last dose of LY3209590 and 5 weeks after the last dose of insulin degludec. Study activities at Visits ED 1 and ED 2 are identical to Week 26 (Visit 20) and Visit 801, respectively. This close follow-up is necessary since LY3209590 has a **CCI** and the switch to an alternative, commercially available insulin must be closely monitored to prevent hypoglycemia due to an accumulation of insulin action.

Participants who discontinue IP prior to the completion of the treatment period will be encouraged to remain in the study and to complete any scheduled study procedures that occur until Visit 20. Participants remaining in the study will receive an appropriate glucose-lowering regimen.

Participants who *discontinue IP for any reason and are unwilling to return for a safety follow-up* visit, will be asked to perform an early termination (ET) visit as their final study visit. At this visit, participants will perform procedures listed in the Schedule of Activities (Section 1.3).

4.2. Scientific Rationale for Study Design

This study will evaluate LY3209590 in patients with T1DM, compared with an active control.

The study will last 26 weeks to have an adequate duration of exposure necessary to assess efficacy and safety of LY3209590.

Insulin degludec is an unblinded active comparator in this study and will be used to compare the effects of LY3209590 on glycemic control, hypoglycemia, and weight gain with a daily basal insulin.

4.3. Justification for Dose

CCI

a single loading dose, followed by weekly dose adjustments is recommended for LY3209590 dosing regimen. The loading dose is determined based on the patient's previously used basal insulin dose, baseline fasting glucose, and available LY3209590 data to inform the **CCI** loading dose strategy. Dose adjustments are based on prior fasting glucose and hypoglycemia events. Alterations to the doses recommended by these dose adjustment algorithms are also under discretion of the investigator and will take hypoglycemia and other study participant safety concerns into account. In case of a deviation from the algorithm-recommended dose, a medical rationale for this deviation must be documented by the principal investigator.

The starting dose for insulin degludec is the same dose as the basal insulin that the study participant used prior to entering the study. The study participant will start a titration phase based on FG and the presence of hypoglycemia or other safety concerns. Dose adjustments will be performed according to a modified Riddle algorithm, which is widely used in clinical trials and clinical practice (Section 10.8).

As it may be desirable to achieve therapeutic goal of LY3209590 in less than 12 weeks with low risk of hyperglycemia, an initiation dose strategy may be appropriate where the first dose sufficient to achieve an efficacious exposure is given initially, followed by individually optimized weekly dose adjustments to achieve target response. Table for Algorithm 1 shows the loading doses, as well as those to be used when adjusting the dose during the dose-individualization visits. See Section 10.8 for description of the dose adjustment algorithms.

Guidance is provided for dosing suggestions for investigators based on FG and hypoglycemia of the study participant (Section 10.8).

Safety of study participants will be closely monitored during the early stages of dose titration to determine whether adjustments to the conversion and dose adjustment algorithm is needed. As additional data emerges, guidance from the sponsor on these dosing algorithms may be modified (Section 10.8).

4.4. End of Study Definition

End of the trial is the date of the last visit or last scheduled procedure shown in the Schedule of Activities (Section 1.3) for the last patient.

5. Study Population

Prospective approval of protocol deviations to recruitment and enrollment criteria, also known as protocol waivers or exemptions, is not permitted.

5.1. Inclusion Criteria

Participants are eligible to be included in the study only if all of the following criteria apply:

Type of Study Participant and Disease Characteristics

- [1] Have a diagnosis of T1DM for at least 1 year. A diagnosis of T1DM is based on medical history with a fasting C-peptide ≤ 0.30 nmol/L at screening or before randomization.
- [2] Have been using MDIs without interruption for at least 3 months prior to screening.

Study Participant Characteristics

- [3a] No male contraception required except in compliance with specific local government study requirements.
- [3b] Female participants:
 - 1) Women of child-bearing potential who are abstinent (if this is complete abstinence, as their preferred and usual lifestyle) or in a same sex relationship (as part of their preferred and usual lifestyle) must agree to either remain abstinent or stay in a same sex relationship without sexual relationships with males. Periodic abstinence (e.g., calendar, ovulation, symptothermal, post-ovulation methods), declaration of abstinence just for the duration of a trial, and withdrawal are not acceptable methods of contraception.
 - 2) Otherwise, women of child-bearing potential participating must agree to use 1 highly effective method (less than 1% failure rate) of contraception, or a combination of 2 effective methods of contraception for the entirety of the study.
 - a) Women of child-bearing potential participating must test negative for pregnancy prior to initiation of treatment as indicated by a negative serum pregnancy test at the screening visit followed by a negative urine pregnancy test within 24 hours prior to exposure.

b) Either 1 highly effective method of contraception (such as combination oral contraceptives, implanted contraceptives or intrauterine device) or a combination of 2 effective methods of contraception (such as male or female condoms with spermicide, diaphragms with spermicide or cervical sponges) will be used. The participant may choose to use a double barrier method of contraception. Barrier protection methods without concomitant use of a spermicide are not a reliable or acceptable method. Thus, each barrier method must include use of a spermicide. It should be noted that the use of male and female condoms as a double barrier method is not considered acceptable due to the high failure rate when these methods are combined.

3) Women not of childbearing potential may participate and include those who are:

- a) infertile due to surgical sterilization (hysterectomy, bilateral oophorectomy, or tubal ligation), congenital anomaly such as mullerian agenesis; or
- b) post-menopausal – defined as either
 - i) A woman at least 40 years of age with an intact uterus, not on hormone therapy, who has cessation of menses for at least 1 year without an alternative medical cause, AND a follicle-stimulating hormone (FSH) >40 mIU/mL; or
 - ii) A woman 55 or older not on hormone therapy, who has had at least 12 months of spontaneous amenorrhea; or
 - iii) A woman at least 55 years of age with a diagnosis of menopause prior to starting hormone replacement therapy.

[4] Are at least 18 years of age, at the time of signing the informed consent.

[5] Have HbA1c values of 5.6% to 9.5% inclusive, as determined by the central laboratory at screening.

[6] Have been treated with a stable regimen of once- or twice-daily insulin glargine (U-100 or U-300), insulin detemir, or insulin degludec (U-100 or U-200) for 3 months prior to screening.

[7] Are currently treated with the same SC rapid-acting analog insulin (insulin lispro U-100 or U-200, insulin aspart, FiAsp, or insulin glulisine) in MDI for at least the last 30 days prior to screening.

[8] Have a body mass index (BMI) $\leq 35 \text{ kg/m}^2$, with no significant weight gain or loss in the past 3 months ($\geq 5\%$).

[9] In the investigator's opinion, are well-motivated, capable, and willing to:

- learn how to self-inject treatment;
- maintain study diaries, as required for this protocol;

- wear study-provided CGM (Dexcom G6) during the complete study duration without interruption and use this device for therapeutic decision-making;
- must have a normal wake/sleep pattern such that midnight to 0600 hours will reliably reflect a usual sleeping period.

[10] In the investigator's opinion, are proficient in:

- counting carbohydrates
- adjusting meal- and correction boluses based on glucose readings with a stable insulin/carbohydrate ratio as well as correction factors
- adjusting insulin and dietary therapy during special situations (e.g., exercise, stress, intermittent diseases)

[11] Are willing and able to follow the visit schedule during the complete duration of the trial.

Informed Consent

[12] Capable of giving signed informed consent as described in Section [10.1](#), which includes compliance with the requirements and restrictions listed in the ICF and in this protocol.

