6.7.1. Treatment after Study Completion

The last study treatment administration for patients treated with LY3209590 will be at Week 25 and for patients treated with insulin degludec the evening before the last study visit at Week 26. The washout of LY3209590 may take up to 10 weeks to complete. Any appropriate basal insulin treatment must therefore be instituted slowly and under regular supervision of BG profiles after discontinuation of LY3209590. Since CCI [REDACTED]

[REDACTED] Therefore, a slow up-titration of another basal insulin is necessary to prevent hypoglycemia due to overlapping insulin action. For example, no insulin would be required until the study participant's FG increases to >100 mg/dL, and then daily basal insulin would be initiated and adjusted based on FG.

Study participants assigned to the insulin degludec treatment group will switch to the basal insulin used before entering the study. If insulin degludec was the pre-study basal insulin, they can continue with the same dose used until Visit 20 of the study. If they switch to another basal insulin (e.g., insulin glargine), study participants should inject a daily dose, which is 20% lower than the last dose of insulin degludec used before Visit 20 and titrate under supervision of the investigator using the country-specific label for their pre-study basal insulin.

7. Discontinuation of Study Intervention and Participant Discontinuation/Withdrawal

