8.3.5. Pregnancy

Pregnancy (maternal or paternal exposure to IP) does not meet the definition of an AE. However, to fulfill regulatory requirements, any pregnancy should be reported following the SAE process described in Section 10.4 and to collect data on the outcome for both mother and fetus.

Details of all pregnancies in female participants and, if indicated, female partners of male participants will be collected after the start of study intervention and until 90 days after the last dose.

If a pregnancy is reported, the investigator should inform the sponsor within 24 hours of learning of the pregnancy and should follow the procedures outlined in Section 10.4.

Abnormal pregnancy outcomes (e.g., spontaneous abortion, fetal death, stillbirth, congenital anomalies, ectopic pregnancy) are considered SAEs.

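### Contraception for women on LY3209590 ends with the study, about 6 weeks after the last dose, although the protocol allows up to 10 weeks for washout

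*Protocol*

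**What the plan says.** - **Contraception rule.** Protocol Section 5.1, criterion [3b] 2), asks for one highly effective method or "a combination of 2 effective methods of contraception for the entirety of the study". It gives no period after the last dose.
- **Women under [3b] 1).** Women who are abstinent or in a same-sex relationship fall under a separate rule. It has no stated end date and says that "declaration of abstinence just for the duration of a trial, and withdrawal are not acceptable methods of contraception".
- **Last dose.** Section 6.7.1: "The last study treatment administration for patients treated with LY3209590 will be at Week 25".
- **Washout.** The same section: "The washout of LY3209590 may take up to 10 weeks to complete". The consequence it draws is that "a slow up-titration of another basal insulin is necessary to prevent hypoglycemia due to overlapping insulin action".
- **End of participation.** Section 4.1.1 plans "a safety follow-up visit approximately 6 weeks after the last dose of LY3209590". This is Visit 801 for completers and ED2 for those who stop study drug early. Participants who stop study drug and will not return for safety follow-up "will be asked to perform an early termination (ET) visit as their final study visit".
- **Pregnancy reporting.** Section 8.3.5 says that pregnancy details "will be collected after the start of study intervention and until 90 days after the last dose".
- **Cross-reference.** Exclusion [27] iii points to Appendix 4 (Section 10.4) for birth control. That appendix defines childbearing potential and sets out pregnancy reporting. It states neither a method nor a duration, so the methods appear only in [3b].

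**The concern.** The protocol treats exposure in pregnancy as something to avoid. Exclusion [27] bars women who are pregnant or intend to become so, and Section 7.2 withdraws a participant who becomes pregnant. Yet the contraception rule lapses at a point unrelated to the last dose, while Section 6.7.1 says that drug may still be clearing. A pregnancy in that interval would be reportable under Section 8.3.5, but nothing in the protocol would have asked the woman to avoid it.

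Elsewhere the protocol does allow for how long LY3209590 persists. Follow-up after the last dose is a week longer than for insulin degludec, and the overdose guidance in Section 8.4 refers to the long action. The contraception rule makes no such allowance. What is at stake is participant safety and internal consistency. The primary analysis and the sample size are not affected.

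**Working it through.** **Inputs**
- Last LY3209590 dose: Week 25 (Section 6.7.1).
- Visit 801: Week 31, window ±3 days (Section 1.3).
- ED1: about 1 week after the last dose. ED2: 5 weeks after ED1. Each has a ±3-day window (Sections 1.3 and 4.1.1).
- Washout: up to 10 weeks = 70 days (Section 6.7.1).
- Pregnancy collection: to 90 days after the last dose (Section 8.3.5).

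**The plan's own figures.** Week 31 − Week 25 = 6 weeks = 42 days, which agrees with Section 4.1.1. Total participation is 2 + 26 + 5 = 33 weeks, which agrees with the synopsis.

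**Gap against washout, Visit 801 last**
- Gap = 70 − days covered = 70 − 42 = 28 days.
- With the ±3-day window and an on-time last dose, 39 to 45 days are covered. The gap is 70 − 45 = 25 to 70 − 39 = 31 days.

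**Gap against washout, ED2 last**
- The central value is again 70 − 42 = 28 days.
- If the ED1 and ED2 windows add, 42 ± 6 = 36 to 48 days are covered. The gap is 70 − 48 = 22 to 70 − 36 = 34 days.
- Section 4.1.1 also lets ED1 take place later if necessary, so this range is indicative only.

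**Final ET visit**
- With ET at t weeks after the last dose, gap = 10 − t weeks.
- The protocol does not fix t. Assuming t from 0 to 6, the gap runs from 10 down to 4 weeks; t = 1 gives 9 weeks.

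**Early stop at Week s, staying to Visit 20 (Week 26)**
- Cover = max(26 − s, 6) weeks; gap = max(10 − cover, 0).
- s ≤ 16: no gap.
- s = 17, 18, 19: gap of 1, 2, 3 weeks.
- s = 20 to 25: gap of 4 weeks.

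**Position against the reporting window.** 90 − 70 = 20 days, so the whole interval from day 42 to day 70 lies inside the period in which pregnancies are collected.

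**The case against.** The strongest reply is that no standard in the documents is breached. No section says that contraception must last until washout is complete. The 10 weeks is an upper bound, given to guide the restart of basal insulin, and Section 6.7.1 does not mention pregnancy. The half-life is blacked out, so exposure after week 6 cannot be judged. Section 2.2 describes the toxicology findings, from a programme that included reproductive studies in rats and rabbits, as target-related only. The consent form, which binds participants under criterion [12], was not available and may already give a period. Appendix 4 follows pregnancies to outcome and covers related serious events after the study.

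All of this is accurate, and it is why the priority is low. It does not remove the point: a stated rule ends while the same protocol says that drug may remain. A fuller consent form would not correct the criterion, and following a pregnancy does not prevent one.

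The study could also be read as the whole trial (Section 4.4). That is strained for an individual's obligation. Women who finish near the end of the trial would still have the gap, and the period would still not follow from the dose.

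A reader might infer two stronger things. One is that the 90 days in Section 8.3.5 sets a contraception requirement, which would make the shortfall 90 − 42 = 48 days. It does not: it is a reporting window, and a reporting window longer than the contraception period is not a contradiction. The other is that the plan exposes fetuses to a known harm. The documents show no such harm.

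**Conclusion.** The point holds as a low-priority gap. For women on LY3209590 who use contraception under [3b] 2) and finish at Visit 801, the requirement stops up to about 28 days (25 to 31) before the longest washout that the protocol allows. The central figure is the same for ED2, with a wider range because two visit windows apply. After a final ET visit the gap is longer, by an amount that the protocol does not fix.

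This rests on three assumptions: that the study means the individual's own participation, that the last dose is given on time, and that washout takes the full 10 weeks. If washout is shorter, the gap shrinks, and at 6 weeks it disappears for those seen at Visit 801 on schedule.

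It would be too broad to infer that every woman in the trial is affected. The point does not reach women under [3b] 1) or the insulin degludec arm. It also does not reach those who stop LY3209590 by Week 16 and stay to Visit 20. The number of women affected is not given.

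**What to change.** In [3b] 2), add that women of childbearing potential assigned to LY3209590 continue contraception until the later of study end or at least 10 weeks after their last LY3209590 dose, including when an ET visit is final. State the same period in Appendix 4, with a reference to the methods in [3b], and align the consent form if it does not already say so. The rule for insulin degludec can stay as it is. The sponsor may prefer 90 days, so that contraception and pregnancy collection share one end point, but the documents do not require that.

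The cost is a wording amendment with ethics approval (Section 10.1.1) and re-consent of current participants (Section 10.1.3). Completers would use contraception for about 4 more weeks, or 48 days more under the 90-day option. The extension would be longer after an early ET visit. No new visit is needed.
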